Aim 2. Determine the predictors of observational and rule-based learning, incorporating subject-specific measures of structural brain damage, aphasia severity, attention, verbal working memory and executive function. We will use regression models to determine predictors of observational learning and rule-based learning, evaluating findings against theoretical frameworks. We predict that preservation of the striatum and selective attention will contribute to observational learning ability. Preservation of the prefrontal cortex, verbal working memory and executive function are expected to contribute to rule-based learning ability.

BACKGROUND AND SIGNIFICANCE

Provide a brief paragraph summarizing prior experience important for understanding the proposed study and procedures.

Aphasia is an impairment in the expression or comprehension of language that results from stroke, traumatic brain injury or progressive neurological disease. Research has shown that speech-language therapy, the treatment for aphasia, can significantly improve people's ability to communicate. However, A major challenge facing the field of aphasia rehabilitation is the variable response to intervention; while some patients respond to therapy, others show limited progress.

Partners Human Subjects Research Application Form Version Date: October 15, 2014 One relatively unexplored possibility is that response to intervention is, in part, due to differences among how patients best learn, which we refer to as learning phenotype. Although learning phenotypes have been used to inform rehabilitation treatments in other domains, treatments for aphasia are currently selected almost exclusively based on language abilities with little to no attention to underlying learning abilities. Our overarching hypothesis is that poor alignment of learning ability and language therapy limits progress and contributes to the variability in outcomes.

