assigned a binary value (1 or 0), are normalized from native to MNI space (a standard brain space utilized in imaging studies). The individualized lesion map is subtracted from each brain region of interest (ROI) to yield the volume of spared tissue per ROI. The percentage of spared tissue in each region is calculated by dividing the volume of spared tissue by the total volume of the MNI atlas ROI. We will use MATLAB to identify the union of lesion maps and anatomical ROIs from the MNI template to compute lesion volume and percent spared tissue for each ROI. Percent spared tissue in ROIs will be entered into regression models evaluating predictors of learning.

Cognitive Linguistic Assessments: Language and cognitive assessments will be scored based on norms and methods of administration and scoring provided in testing manuals and publications.

Composite scores of sustained attention, executive function, and auditory-verbal working memory will be computed for entry into regression models.

Data Analyses: Linear regression models will be run to determine the predictors of learning. Separate models will be examined for SRT observational, AGL observational and rule-based and learning. The dependent variable for SRT observational learning will be Cohen's d effect size for the first round of learning computed in Aim 1. The dependent variable for AGL observational learning will be percent correct in testing computed in Aim 1. The dependent variable for AGL observational learning will be percent accuracy obtained in Aim 1. We anticipate that accuracy rates will fall between .2 and .8 which is recommended if accuracy rates are to be used as a dependent variable for a linear regression. If scores fall outside of this range, we will switch to a logistic regression model where number of successes and the total number of trials are incorporated into the analysis.

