Extensive, partially-overlapping neural networks have been identified to support implicit and rule-based learning. In proposed regression models, we first propose to include percent spared tissue in those ROIs that have shown differential activation in observational versus rulebased learning. Thus, for observational learning, the striatum, which shows enhanced engagement in implicit over rule based learning will be included (e.g. Destrebecqz et al., 2005; Peigneux et al., 2000; Schendan et al., 2003) along with composite scores of visual attention, as attention has been found to be important for implicit learning (e.g. Franklin et al., 2016; Seger 1994). We will evaluate the statistical significance of a regression model with two predictors: percent spared tissue in the striatum and cognitive scores of attention, evaluating the statistical significance of the model and variability accounted for.

For rule-based learning, studies have identified the prefrontal cortex as an important neural substrate that shows increased engagement in rule-based relative to observational learning (e.g. Byrne et al., 2016; Milton et al. 2009; Panuikov & Davis, 2018; Tracey et al., 2003). Verbal working memory and executive functions also play a rule in rule management and shifting (e.g. Carpenter et al., 2016). Thus, we will evaluate the statistical significance of a regression model with three predictors: percent spared tissue in the prefrontal cortex and cognitive scores of working memory and executive function, evaluating the statistical significance of the model and variability accounted for.

Power estimations and justification of sample size. Power analysis for a multiple regression with two predictors was conducted in G*Power to determine a sufficient sample size using an alpha of 0.05. Using an effect size $f^2 = 0.25$, based on correlations of .38 between striatal activation and implicit learning (Peigneux et al., 2000) and on correlation values of .32 between attention and implicit learning from pilot data, with a sample size of 50 we will have power greater than .90 to detect significant effects.

For rule-based learning, a power analysis was conducted in G*Power including 3 predictors. An effect size f² of .28 was estimated based on correlations between prefrontal

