cortex activation and rule-based learning of 0.34 (Paniukov et al., 2018) and correlations between executive functions, attention and learning that range from .25 to.72 (based on Schnyer et al. 2009 and our pilot work). To achieve 85% power with an alpha of .05 a sample size of 49 is necessary.

Additional participants are included in this IRB to account for potential attrition and the possibility that some participants do not learn tasks limiting the interpretability of results.

Briefly describe study procedures. Include any local site restrictions, for example, "Subjects enrolled at Partners will not participate in the pharmacokinetic portion of the study." Describe study endpoints.

Participants who agree to participate and who provide informed consent will perform 3 to 5, sessions up to 2 hours long. Some participants may prefer to schedule testing over a series of several sessions, which will be accommodated. During these sessions, they will complete:

- SRT Observational (implicit) learning task
- AGL Observational (implicit) learning task
- Rule-based learning task
- Cognitive-linguistic assessments
- Brain Scan

Learning tasks are computer based. Tasks involve looking at pictures, shapes. listening to audio instructions and making button presses. Participants will receive audio and visual instructions. They will complete short practice blocks and have the opportunity to ask questions prior to completing tasks.

Observational (implicit) learning tasks (~ 45 mins):

Observational learning will be evaluated using two tasks: SRT observational learning and AGL observational learning.

The SRT Observational learning task is a classic paradigm, which has been integral to the understanding of implicit learning (see Schwarb & Schumacher, 2012). The SRT that we propose to use to characterize observational learning is a replication of classic SRT tasks first described by Nissen and Bullemer (1987), adapted for eye-tracking by Kinder et al. (2008) and piloted by our team in PWA, young adult and older adult controls. During this task:

- Participants will be seated at least 50 cm from a computer screen with their chin resting on a chin rest.
- The chin rest and chair level will be adjusted for comfort
- The eyetracking camera will be focused on one of the participant's eyes (right eye or dominant eye).
- Four geometric shapes will appear on screen
- A target dot will move from shape to shape

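### Aim 2 predicts that each named predictor contributes, but the only stated criterion is whole-model significance and variability explained, which one predictor alone can satisfy

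*Combined protocol and SAP*

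**What the plan says.** Specific Aims, Aim 2, states the hypotheses predictor by predictor. For observational learning: "We predict that preservation of the striatum and selective attention will contribute to observational learning ability". For rule-based learning: "Preservation of the prefrontal cortex, verbal working memory and executive function are expected to contribute to rule-based learning ability".

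The Aim 2 Data Analyses text gives the purpose of the regressions: "Linear regression models will be run to determine the predictors of learning". It calls for separate models for SRT observational, AGL observational and rule-based learning. The observational model has two predictors and is assessed as follows: "percent spared tissue in the striatum and cognitive scores of attention, evaluating the statistical significance of the model and variability accounted for". The rule-based model has three: percent spared prefrontal tissue plus "cognitive scores of working memory and executive function, evaluating the statistical significance of the model and variability accounted for". No test, interval, partial or incremental R-squared, or multiplicity rule for an individual coefficient is stated anywhere.

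The power section gives one effect size per model.
- **Observational:** "Power analysis for a multiple regression with two predictors was conducted in G*Power", using f² = 0.25 based on correlations of .38 (striatum) and .32 (attention). The stated result is that "with a sample size of 50 we will have power greater than .90 to detect significant effects".
- **Rule-based:** three predictors and f² = .28, based on a prefrontal correlation of 0.34 and correlations between "executive functions, attention and learning that range from .25 to.72". The stated result is N = 49 for 85% power at alpha .05.

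**The concern.** The null hypothesis of the model F test is that all slopes are zero. Rejecting it says that something in the set is related to learning, but not which predictor. Aim 2 asks which. The stated criterion therefore does not answer the stated question, even though the same fitted model contains the answer.

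Two things are at stake. First, a significant model could be reported in support of the striatal or prefrontal prediction when a cognitive score carries the whole fit; the structural imaging enters these models through those two brain predictors. Second, the quoted power could be taken as the chance of confirming each predictor, which is considerably lower.

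**Working it through.** **Method.** Power is from the noncentral F distribution, the usual calculation for fixed-predictor regression. Noncentrality is λ = f² × N, the degrees of freedom are u and N − p − 1, and alpha is .05. For the whole model, u = p (the number of predictors) and f² = R²/(1 − R²). For one coefficient, u = 1 and f² = (R² full − R² without it)/(1 − R² full).

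**1. The plan's own figures.**
- Rule-based, whole model, f² = .28, p = 3: power is .858 at N = 49 and just under .85 (.8497) at N = 48. So 49 is the smallest N for 85%, an exact match. A one-coefficient test with the same f² would need only N = 35. This is a whole-model calculation.
- Observational, whole model, f² = .25, p = 2, N = 50: power is .875, not above .90; N = 54 would be needed. A one-coefficient test given the entire f² = .25 yields .934, but that requires a partial correlation of √.20 = .447, above both stated correlations. Entering the two correlations as uncorrelated gives R² = .38² + .32² = .1444 + .1024 = .2468, f² = .328 and whole-model power .949.

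The test used for the observational figure cannot be identified from the text. On every reading, the effect size combines both predictors.

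**2. One predictor carrying the model.** Set the other observational slope to zero, N = 50, p = 2.
- Attention only: f² = .1024/.8976 = .114, λ = 5.70, power .53.
- Striatum only: f² = .1444/.8556 = .169, λ = 8.44, power .71.

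More generally, whole-model power depends only on total f², not on how it is shared. If all of f² = .28 came from one rule-based predictor (r = √(.28/1.28) = .47), whole-model power would still be .858.

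**3. Power per predictor, observational, N = 50.** With r₁ = .38, r₂ = .32 and predictor correlation ρ, R² = (r₁² + r₂² − 2r₁r₂ρ)/(1 − ρ²). The documents do not give ρ, so it is varied as an assumption.

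| ρ | R² | f² striatum | power | f² attention | power |
|---|---|---|---|---|---|
| 0 | .247 | .192 | .86 | .136 | .72 |
| .24 | .200 | .122 | .68 | .070 | .45 |
| .5 | .167 | .077 | .49 | .027 | .21 |

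The middle row is the value of ρ at which the two stated correlations reproduce the plan's f² = .25. Simulation there (40,000 runs, normally distributed predictors) gave .65 and .43. The model was significant in 85% of runs and both coefficients in 25%; about 71% of the significant models did not have both coefficients significant.

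**4. Power per predictor, rule-based, N = 49.** R² = .28/1.28 = .219. Assume an equal split over three uncorrelated predictors: f² = (.219/3)/(1 − .219) = .093 each, power about .55. Weaker or correlated predictors would have less.

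**5. Multiplicity.** The named coefficients number 2 (SRT) + 2 (AGL) + 3 (rule-based) = 7. If all seven were null and independent, testing each at .05 gives a chance of 1 − .95⁷ = .30 of at least one false positive. With Bonferroni (.05/7 = .0071), the ranges in step 3 fall to about .61–.21 for the striatum and .43–.06 for attention, and the .55 in step 4 to about .26.

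**The case against.** The strongest reply is that the text is headed as a brief overview, that its declared purpose is to determine predictors, and that coefficients appear in any regression output. A reader might infer from the model-level wording that no coefficient will be tested, or that a significant F will be claimed as support for every predictor. The documents say neither. What is missing is a stated criterion for the individual predictors, and that is all this point asserts. The reply does not remove it, because the only criterion written down is for the model, and it leaves open how coefficients will be judged and how error is controlled.

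A reader might also infer that both power statements are shown to be omnibus calculations. Only the rule-based one is, by exact match; the observational figure does not reproduce as a whole-model test at f² = .25. It still powers no single predictor.

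A more dramatic illustration is tempting: one rule-based predictor at r = .72 would make the model significant almost always (above .999 at N = 49). That correlation implies f² = 1.08, nearly four times the planned .28, and the .25 to .72 range is not specific to any predictor in the rule-based model. It should not carry the argument.

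Finally, this is a cross-sectional, non-treatment study, and the coefficients can be recovered from the same fit. That bears on cost and urgency, not on whether the rule fits the aim.

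**Conclusion.** The concern holds in this form: Aim 2 makes predictor-level predictions, the only stated criterion is at model level, and no predictor has its own effect size or power. One observational predictor alone would make its model significant with probability .53 or .71 at the plan's own correlations.

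Per-predictor power at N = 50 is about .86 to .49 for the striatum and .72 to .21 for attention, unadjusted. These ranges assume that the stated correlations are true for the study's own measures and that the two predictors correlate between 0 and .5. The rule-based figure of about .55 at N = 49 assumes an equal split over uncorrelated predictors and is an illustration only. That the observational power comes to .875 rather than above .90 is a smaller, separate discrepancy.

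**What to change.** In the Aim 2 Data Analyses text:
- Base the conclusion about each named predictor on its own two-sided coefficient test, with estimate, 95% CI and partial R-squared. Give the equivalent quantities if the planned switch to logistic regression is used.
- State a multiplicity rule across the seven coefficients, or say which of them are confirmatory and adjust over those.
- Keep the model F test and R-squared as supporting results.

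In the power section:
- Label the stated power as whole-model power, and correct or explain the observational figure.
- Give per-predictor power as a range, with the assumed predictor correlation shown and the multiplicity rule applied.

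The cost is wording and a short recalculation; no new data or procedures are needed. The drawback is that the stated power becomes less favourable, and some predictor-level results may have to be presented as estimates with intervals rather than as well-powered tests.

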During aphasia rehabilitation, patients are guided to relearn language, reaccess language or regain functional use of language via therapies that involve stimuli, tasks, cues and feedback (see Horton, 2006). Consequently, the process of therapy implicitly engages many mechanisms of learning that need to be systematically considered in aphasia. Evidence is emerging to suggest that nonlinguistic learning is impaired in individuals with aphasia (Schuchard & Thompson, 2014; [name] & Kiran, 2013a; [name] & Kiran, 2013b); and furthermore, that PWA develop strategies less consistently and less effectively than non brain-damaged controls ([name] & Kiran, 2015). We suggest that the contribution of underlying cognitive systems is essential to relearning in aphasia and that understanding the behaviors associated with learning are critical for our understanding of the mechanisms of therapy and ways to better tailor treatment to individuals.

In aphasia, little is understood about how task and treatment manipulations impact patient behaviors and progress with therapy. We propose to thoroughly examine the behaviors of learning and the cognitive-linguistic and lesion characteristics that relate to learning, to characterize a phenotype of learning for individuals with aphasia, setting the foundations for intervention studies aimed at individually tailoring treatment and improving the predictability of outcomes.

RESEARCH DESIGN AND METHODS

Briefly describe study design and anticipated enrollment, i.e., number of subjects to be enrolled by researchers study-wide and by Partners researchers. Provide a brief summary of the eligibility criteria (for example, age range, gender, medical condition). Include any local site restrictions, for example, "Enrollment at Partners will be limited to adults although the sponsor's protocol is open to both children and adults."

Study Design

In this cross-sectional study, 75 participants will complete language and cognitive assessments and behavioral tests of learning. A subset of participants will also complete a structural magnetic resonance imaging (MRI) scan to obtain structural brain images.

Sessions 1 & 2 described above, may take 3 sessions. If an additional session is needed, participants may complete this session in person or over Zoom based on preference. Session 3 described above, may be broken into 2 sessions based on participant scheduling preference.

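### At its own inputs (f² = .25, two predictors, N = 50, alpha .05) the observational-learning model has power .875, not above .90

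*Combined protocol and SAP*

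**What the plan says.** The section on power estimations and justification of sample size gives the observational-learning calculation in full except for the name of the test. It states that "Power analysis for a multiple regression with two predictors was conducted in G*Power to determine a sufficient sample size using an alpha of 0.05". The effect size is given as f² = .25, "based on correlations of .38 between striatal activation and implicit learning" and on "correlation values of .32 between attention and implicit learning from pilot data". The conclusion is that "with a sample size of 50 we will have power greater than .90 to detect significant effects".

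The inference that this supports is described under Data Analyses (Aim 2): "We will evaluate the statistical significance of a regression model with two predictors", namely spared striatal tissue and attention. Significance is to be judged for the model, together with the variability it explains.

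The same power section has a second calculation, for the three-predictor rule-based model, with f² = .28: "To achieve 85% power with an alpha of .05 a sample size of 49 is necessary".

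**The concern.** The number of predictors, alpha, effect size and N are all stated, so the power can be recomputed. For the model-level test that the plan describes, it does not come out above .90. At least one element of the sentence must therefore be wrong or undisclosed: the effect-size label, the test, or the power.

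This sentence is the sample-size justification for the observational-learning side of Aim 2, where SRT and AGL learning are modelled separately. As written, a reader cannot tell whether 50 analysable participants give power of about .88 or about .95.

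**Working it through.** **Inputs.** From the power section: k = 2 predictors, alpha = .05, f² = .25, N = 50, stated power above .90. For the companion calculation: k = 3, f² = .28, alpha = .05, 85% power, N = 49. From Data Analyses: the overall model is tested.

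**Formula.** For the overall test of R² = 0, the numerator df is k, the denominator df is N − k − 1, and the noncentrality is λ = f² × N. Power = 1 − P(F′ ≤ F_crit), where F′ is noncentral F and F_crit is the central 95% point.

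**Step 1: the plan's companion figure.** With k = 3 and f² = .28:
- N = 48: power .8497, just short of 85%.
- N = 49: df (3, 45), λ = .28 × 49 = 13.72, power .858.

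The smallest N for 85% is 49, exactly as stated. The alternatives do not fit. A one-df test would need only N = 35, and reading .28 as R² (f² = .28/.72 = .389) would need only N = 36. The companion figure therefore points to the overall F test on the f² scale.

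**Step 2: the two-predictor figure.** With k = 2, f² = .25 and N = 50: df (2, 47), λ = .25 × 50 = 12.5, F_crit = 3.195, **power .875**. A simulation with 40,000 replicates gave .876.
- Rounding of f² does not explain the gap: .245 gives .868 and .255 gives .882.
- Treating the predictors as random lowers power to about .85.
- N = 53 gives .895 and N = 54 gives .902, so .90 needs 54.
- At N = 50, power .90 needs f² = .270.

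**Step 3: what would give more than .90 at N = 50.**

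| Reading | f² | Power |
|---|---|---|
| .25 is R²: f² = .25/.75 | .333 | .952 |
| R² = .38² + .32² = .1444 + .1024 = .2468 (uncorrelated predictors): f² = .2468/.7532 | .328 | .949 |
| One-df coefficient test, df (1, 47) | .25 | .934 |
| Overall test at alpha .10 (contradicts the stated .05) | .25 | .932 |

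**Step 4: can f² = .25 be right for these correlations?** With predictor correlation r (not given in the document, so assumed here), R² = (.38² + .32² − 2 × .38 × .32 × r)/(1 − r²).

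| Assumed r | R² | f² | Power at N = 50 |
|---|---|---|---|
| 0 | .247 | .328 | .949 |
| .10 | .225 | .290 | .920 |
| .20 | .206 | .260 | .888 |
| .24 | .200 | .250 | .875 |
| .30 | .191 | .236 | .855 |

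So .25 is either close to R² for uncorrelated predictors or the correct f² for predictors correlated at about .24. The document does not show which was meant.

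**The case against.** The strongest reply is that only a label may be wrong. The squared correlations sum to .247, very close to .25. If that value entered G*Power as R² and was then written up as f², power is about .95 and the claim is true. This reply stands as a possibility, so the finding is that the stated inputs do not give the stated power; it does not show that the study has less power than claimed. It does not rescue the sentence, because f² is what is printed, .25 can also be a correctly derived f², and the companion calculation uses the f² scale.

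A second reply is that the sentence speaks of detecting effects and Aim 2 concerns individual predictors, so a coefficient test (.934) may have been intended. That is arguable, but the plan evaluates the model as a whole and the companion figure does not fit a one-df test. All of f² = .25 would also have to belong to one predictor. With uncorrelated predictors the separate contributions are .1444/.7532 = .192 and .1024/.7532 = .136, with power .858 and .724.

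A third reply is that the gap hardly matters, and this largely stands. The plan itself accepts 85% for the rule-based model. Enrolment is 75, 54 is 72% of that (54/75), and "Additional participants are included in this IRB to account for potential attrition". This limits the weight of the point but does not make the stated figure correct.

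**Conclusion.** The concern holds. At f² = .25, N = 50 and alpha .05, the planned overall test of the two-predictor model has power .875. The type II error is 12.5% rather than under 10%, a shortfall of 2.5 points, equivalent to four analysable participants (54 instead of 50).

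This rests on the usual fixed-predictor noncentral F calculation, which reproduces the plan's other sample size exactly, and on taking the printed f² at face value. If R² = .25 was meant, power is .95 and the error lies in the effect-size label. Either way the sentence needs correcting. The design is not undermined, and .875 would be acceptable by the plan's own 85% standard.

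**What to change.** Name the G*Power test used and state whether .25 is f² or R². Then restate the sentence in whichever form applies:

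- f² = .25, N = 50, alpha .05: power .875 (about .88) for the overall two-predictor model; or
- R² = .25, f² = .33, N = 50, alpha .05: power .95 for the overall two-predictor model. If R² was obtained by summing the squared correlations, say that the predictors were assumed uncorrelated.

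If a one-df coefficient test was run, say so, identify the predictor to which f² = .25 belongs, and report the overall-model power of .875 beside it. If power of .90 at f² = .25 is to be kept as the target, the analysable number becomes 54.

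The cost is a text correction. No analysis changes and no added enrolment is needed; the stated power either falls slightly to .875 or stays above .90.
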